If a subject met the censoring criteria for CD related concomitant therapy during Study M14-115, all binary efficacy endpoints will be No in Study M14-347, all observed values in Study M14-347 will be replaced by Study M14-115 Baseline values.

Dose Escalation

Subjects who had dose escalated to 40 mg ew will be censored for efficacy assessments (i.e., will be considered non-responders for categorical endpoints and will have

Study M14-115 Baseline values carried forward for non-categorical assessments) from that point through the end of the study.

Definition of Missing Data Imputation

Missing data imputation will be done only for efficacy variables (categorical and continuous variables). For the analysis other than efficacy, no imputation will be done for missing values.

Non-Responder Imputation (NRI)

The NRI approach is used for binary efficacy data. These variables can take values of 'Achieved' or 'Not Achieved' or may be missing for any reason including discontinuation from study. According to the NRI imputation approach, all missing values will be considered as 'Not Achieved.'

Observed Case (OC)

Observed case analysis will be performed such that missing values will not be imputed. However, all observed values will be replaced by Study M14-115 Baseline value once subjects met the censoring criteria for CD-related concomitant therapy or dose escalation, whichever is earlier.

Last Observation Carried Forward (LOCF)

For all variables (categorical variables and continuous variables), the following rules will be used for the LOCF approach:

1. Baseline and Pre-Baseline values will not be used to impute the missing Post-Baseline values.
2. Missing values after Study Day 1 will be imputed using the latest non-missing values after Day 1 and prior to the missing value. If there are no non-missing values after Baseline, then the LOCF value will be missing.

Rule for CDAI Calculation

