- Change in European Quality of Life 5 Dimensions (EQ-5D) from Study M14-115 Baseline over time.
- Change in CDAI from Study M14-115 Baseline over time.
- Change in SFPS from Study M14-115 Baseline over time.
- Change in Abdominal Pain Rating Scale score from Study M14-115 Baseline over time.
- Change in each CDAI component subscore (number of liquid or very soft stools, abdominal pain rating, general well-being, CD related complications, anti-diarrhea use, abdominal mass, hematocrit, body weight) from Study M14-115 Baseline over time.
- Time to first dose escalation.

- Proportion of subjects who require weekly dosing at Week 1 of Study M14-347.
- Proportion of subjects with major CD related event (e.g., hospitalization, bowel surgery, abscess drainage).
- Proportion of subjects with CD related hospitalization.
- Proportion of subjects with CD related surgery.
- Proportion of subjects requiring dose escalation to weekly dosing during this study.
- Proportion of subjects with no draining fistulas over time among subjects with draining fistula at Study M14-115 Baseline.
- Proportion of subjects in each treatment group with > 50% reduction from Baseline of Study M14-115 in the number of draining fistulas over time among subjects with draining fistula at Study M14-115 Baseline.
- Resolution of extraintestinal manifestations over time.
- Proportion of subjects who achieve symptomatic remission, defined as average daily stool frequency ≤ 1.5 (and not worse than Study M14-115 Baseline) and average daily abdominal pain ≤ 1.0 (and not worse than Study M14-115 Baseline) over time among subjects with Study M14-115 Baseline average daily stool frequency ≥ 2.5 or average daily abdominal pain ≥ 2.0 .
- Proportion of subjects who achieve symptomatic remission, defined as average daily stool frequency ≤ 2.8 (and not worse than Study M14-115 Baseline) and average daily abdominal pain ≤ 1.0 (and not worse than Study M14-115 Baseline) over time among subjects with Study M14-115 Baseline average daily stool frequency ≥ 4.0 or average daily abdominal pain ≥ 2.0 .
- Proportion of subjects who achieve symptomatic response, defined as average daily stool frequency at least 30% reduction from Study M14-115 Baseline and average daily abdominal pain not worse than Study M14-115 Baseline or average daily abdominal pain at least 30% reduction from Study M14-115 Baseline and average daily stool frequency not worse than Study M14-115 Baseline, over time.

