For categorical additional efficacy endpoints, the two-sided 95% confidence interval for the proportions will be provided. The NRI method will be used for subjects with missing data at the time point evaluated. The LOCF method will also be used as the sensitivity analyses.

For continuous additional efficacy endpoints, change from Study M14-115 Baseline will be summarized by descriptive statistics using mean, standard deviation, minimum, median and maximum. Both LOCF and observed case analyses will be performed.

For time to event additional efficacy endpoints, the number of event and the 25th, median, and 75th percentiles of time to event will be estimated by the product limit method. The 95% CI for the median time-to-event will also be provided if applicable.

The time to first occurrence of event will be calculated as (first occurrence of event date or censoring date – date of first dose of the treatment during this study + 1). Subjects who did not experience the event prior to discontinue or complete the study will be censored at the date the last assessment was taken. For the endpoint of time to dose escalation, subjects without experiencing an event will be censored at the last available dose date.

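### The SAP's responder-type rules have no exemption for major CD events, CD hospitalization and CD surgery, and no planned analysis of these endpoints allows for follow-up time

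*SAP*

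**What the plan says.** SAP 6.0 limits imputation to efficacy: "Missing data imputation will be done only for efficacy variables (categorical and continuous variables". Within that scope, "The NRI approach is used for binary efficacy data". Whatever the cause of the gap, including leaving the study, the rule is that "all missing values will be considered as 'Not Achieved".

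Among the additional efficacy variables, SAP 10.3 lists "Proportion of subjects with major CD related event (e.g., hospitalization, bowel surgery, abscess drainage". It also names hospitalization and surgery for CD as two endpoints of their own, and adds one on dosing: "Proportion of subjects requiring dose escalation to weekly dosing during this study". For categorical additional endpoints it then states: "The NRI method will be used for subjects with missing data at the time point evaluated". LOCF is the sensitivity analysis. Neither section separates favourable from unfavourable endpoints.

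Three further rules in SAP 6.0 act on binary or categorical efficacy endpoints:

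- Subjects who met the steroid censoring criteria in Study M14-115 have every binary efficacy endpoint set to No in Study M14-347.
- Subjects who start systemic steroids, or exceed their M14-115 Baseline dose, become non-responders from that point on.
- Subjects who escalate to weekly dosing are treated in the same way.

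SAP 6.0 sends CD hospitalizations and major CD events to adjudication. SAP 10.3 gives a product-limit analysis to time-to-event endpoints, and the only one listed there is time to first dose escalation.

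**The concern.** Non-responder imputation is conservative for remission because unknown status is scored as the bad outcome. For a hospitalization, a bowel operation or a major CD event it works the other way: unknown status is scored as the good outcome. LOCF carries 'no event' forward and errs in the same direction.

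Withdrawal is plausibly related to these outcomes. SAP 8.0 lists lack of efficacy and need for alternative therapy as reasons for stopping. After the discontinuation visit the only planned contact is the telephone call about 70 days after the last dose, waived for anyone who starts commercial adalimumab (Protocol 5.4.1 and 6.4).

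The other rules go further, because they act on observed data. A recorded hospitalization in a subject who met the M14-115 steroid criteria would be reported as No. For a subject who escalates or starts steroids, it is unclear what 'non-responder' means on an event endpoint. At stake is whether the reported 40-week event rates can be read as 40-week risks.

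**Working it through.** **Which rule reaches which endpoint.**

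| Rule | Written scope | Effect on an event endpoint if followed literally |
|---|---|---|
| NRI (SAP 6.0, 10.3) | binary efficacy data | unknown becomes no event |
| LOCF (SAP 6.0, 10.3) | all efficacy variables | last 'no event' carried forward |
| M14-115 steroid rule (SAP 6.0) | all binary efficacy endpoints | observed event becomes No |
| Escalation and on-study steroid rules (SAP 6.0) | categorical endpoints | 'non-responder', meaning undefined for an event |

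**Size.** The plan states no event rate, withdrawal rate or sample-size calculation, so there is no figure to reproduce. The following are assumptions: 40-week risk in completers p = 0.10; fraction withdrawing w = 0.15, 0.25 or 0.35, uniformly over 40 weeks; constant hazard; hazard in withdrawers r = 1 or 3 times that in completers. Time is scaled so that 40 weeks = 1, and h = -ln(0.90) = 0.1054.

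- Risk with full follow-up: (1-w)p + w[1 - exp(-rh)]
- Crude proportion, capture ending at withdrawal: (1-w)p + w × mean over t of [1 - exp(-rht)], where the mean is 1 - [1 - exp(-rh)]/(rh)
- Crude proportion with 70-day capture: the same, with t replaced by min(t + 0.25, 1), since 70/280 days = 0.25

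The crude formulas count events that occur before withdrawal.

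Worked for w = 0.25, r = 1: the mean is 1 - 0.100/0.1054 = 0.051, so crude = 0.075 + 0.25 × 0.051 = 8.8%, against 10.0%.

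Worked for w = 0.25, r = 3: the mean is 1 - 0.271/0.3161 = 0.143, so crude = 0.075 + 0.25 × 0.143 = 11.1%. Full follow-up gives 0.075 + 0.25 × 0.271 = 14.3%.

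| r | w | Full follow-up | Crude, no later capture | Relative shortfall | Crude, 70-day capture | Relative shortfall |
|---|---|---|---|---|---|---|
| 1 | 15% | 10.0% | 9.3% | 7% | 9.6% | 4% |
| 1 | 25% | 10.0% | 8.8% | 12% | 9.3% | 7% |
| 1 | 35% | 10.0% | 8.3% | 17% | 9.0% | 10% |
| 3 | 15% | 12.6% | 10.6% | 15% | 11.5% | 8% |
| 3 | 25% | 14.3% | 11.1% | 22% | 12.5% | 12% |
| 3 | 35% | 16.0% | 11.5% | 28% | 13.5% | 15% |

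**Different withdrawal model.** With constant, independent event hazard l and withdrawal hazard m, the crude proportion is [l/(l+m)] × [1 - exp(-(l+m))]. At 10% risk and 10%, 20% or 30% withdrawal it is 9.5%, 9.0% or 8.4%. Among the 252 enrolled subjects, that is 23.9, 22.6 or 21.3 counted instead of 25.2. The direction is the same.

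**What Kaplan-Meier recovers.** With r = 1, censoring at withdrawal recovers 10.0%. With r = 3, the pooled hazard averages h and 3h over those still at risk, with weights (1-w)exp(-hs) and w(1-s)exp(-3hs) at time s. Integrating it gives 11.4%, 12.4% and 13.5%, against 12.6%, 14.3% and 16.0%. Kaplan-Meier therefore closes only part of the gap when withdrawal is informative.

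**The case against.** The strongest reply is that non-responder imputation was never meant for these endpoints. SAP 10.3 ties it to a time point evaluated, these endpoints have none, and 'achieved' is response language. They are ever/never counts, and a crude ITT proportion gives the same number with or without imputation. This largely stands. It moves the main fault from imputation to a proportion that ignores follow-up, but the SAP contains no exemption and a programmer following it literally would apply the rules. It also does not answer the M14-115 steroid rule, which says all binary efficacy endpoints.

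Other stronger readings are tempting but are not supported:

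- *Dose escalation is biased in the same way.* It already has a product-limit analysis censored at last dose, and a subject who has left the study cannot escalate. Its crude proportion is the on-study incidence. What is missing is a Week 40 figure, since the planned output is the number of events, quartiles and a CI for the median.
- *These are the only hard long-term outcomes.* The primary endpoint is centrally read endoscopy, and deaths and SAEs are tabulated.
- *Safety tables are affected.* SAP 6.0 bars imputation outside efficacy, and SAP 11.2.2.9 plans event rates per 100 patient-years. Those rates cover TEAE overviews, SOC and PT, so they do not replace the adjudicated CD endpoints.
- *More dropout makes the reported rates look better.* With r = 3 the crude rate rises with withdrawal, from 10.6% to 11.5%. What widens is the gap to the full-follow-up risk.

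It is also fair that nothing is tested (SAP 10.1) and there is no comparator arm, so no decision rule depends on these rates.

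**Conclusion.** The concern holds for major CD event, CD hospitalization and CD surgery, in two parts. First, the responder-type rules reach these endpoints by their written scope and, followed literally, score unknown status as favourable and override some observed events. Second, even if the rules are set aside, a crude proportion understates the 40-week risk and no planned analysis of these endpoints corrects for follow-up.

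The relative understatement is about 4-15% if all events to 70 days after the last dose are captured and feed these endpoints, and 7-28% if none after withdrawal are. Both ranges rest on the assumed rates above. The size of the override effect cannot be estimated, because the documents do not say how many subjects met the steroid criteria or escalated.

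A reader might infer that the SAP expressly imputes hospitalizations as absent, or that imputation alone creates the bias. The documents support neither: the first follows only from a general rule without an exception, and the second fails because the crude proportion behaves in the same way. Priority is modest.

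**What to change.** In SAP 10.3:

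1. State that the three endpoints are exempt from NRI, LOCF and the steroid and escalation censoring rules of SAP 6.0, and that every observed adjudicated event counts. State the observation window, including whether events reported at the 70-day call are included.
2. For each endpoint, report the crude count and the Kaplan-Meier cumulative incidence at Week 40 with a 95% CI, censored at end of observation.
3. As sensitivity, report a composite of event or withdrawal for lack of efficacy, since Kaplan-Meier does not remove informative censoring. Label it as a composite, because it no longer estimates hospitalization or surgery alone.
4. For dose escalation, add only the Week 40 estimate from the product-limit curve already planned.

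The cost is a few sentences and a few extra tables. The method is already in the SAP and adjudication is already planned. The reported rates would be somewhat less favourable.

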5.3.3.1 Primary Efficacy Variables

Proportion of subjects with endoscopic improvement, defined as an SES-CD \leq 4 with an Ulcerated Surface subscore no greater than 1 in any segment, at Week 40 among subjects with endoscopic improvement at Week 0 of Study M14-347.

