For Study M14-347, both Roche and Abbott platform are used to measure hs-CRP. The study team has decided to use Abbott platform for CSR analysis. If hs-CRP was measured by Roche platform only, the value will be converted to Abbott equivalent by a conversion factor.

Definition of Endoscopic Improvement

SES-CD \leq 4 and at least two point reduction from Study M14-115 Baseline and no subscore > 1 in any individual variable.

Definition of CDAI Remission

CDAI $<$ 150

Definition of SFPS Remission

SFPS $<$ 50

Definition of CDAI Response

Decrease in CDAI \geq 70 points from Study M14-115 Baseline

Definition of Enhanced CDAI Response

Decrease in CDAI \geq 100 points from Study M14-115 Baseline

Definition of Endoscopic Response

Decrease in SES-CD $>$ 50% from Study M14-115 Baseline

Definition of IBDQ Response

Increase in IBDQ \geq 16 from Study M14-115 Baseline

Definition of IBDQ Remission

IBDQ \geq 170

Definition of Symptomatic Remission

Average daily stool frequency \leq 1.5 and not worse than Study M14-115 Induction baseline AND average daily abdominal pain \leq 1.0 and not worse than Study M14-115 Induction baseline.

Definition of Symptomatic Response

Average daily stool frequency at least 30% reduction from Study M14-115 Induction baseline and average daily abdominal pain not worse than Study M14-115 Induction baseline OR average daily abdominal pain at least 30% reduction from Study M14-115 Induction baseline and average daily stool frequency not worse than Study M14-115 Induction baseline.

Discontinued Corticosteroid Use at Each Visit Among Subjects Who Used Corticosteroids at Week 0 of Study M14-347

Discontinued steroid use at each visit is based on the steroid use on the date of CDAI measurement for that visit. If the subject has no CDAI for the visit, the steroid use on the nominal day for that visit ([Table 3](#)) will be evaluated.

If a subject discontinued the study, 'discontinued corticosteroid use' will be classified as No from that point through the end of the study.

If a subject met censoring criteria for CD-related concomitant therapy or dose escalation, whichever is earlier, 'discontinued steroid use' will be classified as No from that point through the end of the study.

EuroQol-5D-5L (EQ-5D)

EQ-5D is a standardized measure of health status developed by the EuroQol Group in order to provide a simple, generic measure of health for clinical and economic appraisal.

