10.2 Primary Efficacy Analyses

The primary efficacy variable is the proportion of subjects with endoscopic improvement at Week 40 among subjects with endoscopic improvement at Week 0 of Study M14-347.

A two-sided 95% confidence interval will be calculated for ITT analysis set. Missing SES-CD at Week 40 will be imputed using non-responder imputation (NRI) approach. The LOCF method will be used as the sensitivity analyses.

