10.3 Additional Efficacy Analyses

For additional efficacy endpoints, the baseline is defined as the Baseline in Study M14-115. The additional efficacy variables are listed as below.

- Proportion of subjects with CDAI remission (CDAI < 150) over time among subjects with CDAI remission at Week 0 of Study M14-347.
- Proportion of subjects with endoscopic improvement, defined as an SES-CD ≤ 4 and at least 2 point reduction versus Study M14-115 Baseline and no subscore greater than 1 in any individual variable at Week 40.
- Proportion of subjects with CDAI remission (CDAI < 150) over time.
- Proportion of subjects with CDAI < 150 at Week 40 and SES-CD ≤ 4 and at least a 2 point reduction versus Study M14-115 Baseline and no subscore greater than 1 in any individual variable at Week 40 among subjects with CDAI < 150 at Week 0 and SES-CD ≤ 4 and at least a 2 point reduction versus Study M14-115 Baseline and no subscore greater than 1 in any individual variable at Week 0 of Study M14-347.
- Proportion of subjects with CDAI < 150 at Week 40 and SES-CD ≤ 4 and at least a 2 point reduction versus Study M14-115 Baseline and no subscore greater than 1 in any individual variable at Week 40.
- Proportion of subjects with endoscopic response at Week 40 among subjects with endoscopic response at Week 0 of Study M14-347.
- Proportion of subjects with endoscopic response at Week 40.
- Change from Study M14-115 Baseline in fecal calprotectin level over time.

- Proportion of subjects with hs-CRP < 5 mg/L and fecal calprotectin < 250 µg/g over time among subjects with hs-CRP < 5 mg/L and fecal calprotectin < 250 µg/g at Week 0 of Study M14-347.
- Proportion of subjects with hs-CRP < 5 mg/L and fecal calprotectin < 250 µg/g over time.
- Proportion of subjects with CDAI < 150, hs-CRP < 5 mg/L, and fecal calprotectin < 250 µg/g over time among subjects with CDAI < 150, hs-CRP < 5 mg/L, and fecal calprotectin < 250 µg/g at Week 0 of Study M14-347.
- Proportion of subjects with CDAI < 150, hs-CRP < 5 mg/L, and fecal calprotectin < 250 µg/g over time.

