- Proportion of subjects with SES-CD ≤ 3 and at least 2 point reduction versus Study M14-115 Baseline and no subscore greater than 1 in any individual variable at Week 40 among subjects with SES-CD ≤ 3 and at least 2 point reduction versus Study M14-115 Baseline and no subscore greater than 1 in any individual variable at Week 0 of Study M14-347.
- Proportion of subjects with SES-CD ≤ 3 and at least 2 point reduction versus Study M14-115 Baseline and no subscore greater than 1 in any individual variable at Week 40
- Proportion of subjects with SES-CD = 0 at Week 40 among subjects with SES-CD = 0 at Week 0 of Study M14-347.
- Proportion of subjects with SES-CD = 0 at Week 40.
- Proportion of subjects with a decrease of SES-CD ≥ 3 points from Study M14-115 Baseline at Week 40 among subjects with a decrease of SES-CD ≥ 3 points from Study M14-115 Baseline at Week 0 of Study M14-347.
- Proportion of subjects with a decrease of SES-CD ≥ 3 points from Study M14-115 Baseline at Week 40.
- Proportion of subjects with a decrease in SES-CD $> 50\%$ from Study M14-115 Baseline (or for subjects with an SES-CD of 4 at Study M14-115 Baseline, at least a 2-point reduction from Study M14-115 Baseline) at Week 40 among

subjects with a decrease in SES-CD > 50% from Study M14-115 Baseline (or for subjects with an SES-CD of 4 at Study M14-115 Baseline, at least a 2-point reduction from Study M14-115 Baseline) at Week 0 of Study M14-347.

- Proportion of subjects with a decrease in SES-CD > 50% from Study M14-115 Baseline (or for subjects with an SES-CD of 4 at Study M14-115 Baseline, at least a 2-point reduction from Study M14-115 Baseline) at Week 40.
- Change from Study M14-115 Baseline in hs-CRP level over time.
- Proportion of subjects with Inflammatory Bowel Disease Questionnaire (IBDQ) response (decrease \geq 16 points from Study M14-115 Baseline) over time among subjects with Inflammatory Bowel Disease Questionnaire (IBDQ) response (decrease \geq 16 points from Study M14-115 Baseline) at Week 0 of Study M14-347.
- Proportion of subjects with Inflammatory Bowel Disease Questionnaire (IBDQ) response (decrease \geq 16 points from Study M14-115 Baseline) over time.
- Proportion of subjects with IBDQ remission (IBDQ \geq 170 points) over time among subjects with IBDQ remission (IBDQ \geq 170 points) at Week 0 of Study M14-347.
- Proportion of subjects with IBDQ remission (IBDQ \geq 170 points) over time.
- Change in WPAI from Study M14-115 Baseline over time.

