12.0 Summary of Changes

12.1 Summary of Changes Between the Latest Version of Protocol and the Current SAP

The following efficacy variables are mentioned in the protocol but will not be summarized as they were removed from Study M14-115 protocol:

Proportion of subjects with predicted endoscopic improvement at Week 40, using the 3 definitions and equations.

Correlation between actual SES-CD and Predicted SES-CD:

In addition, change in Bristol Stool Scale score from Baseline over time will not be summarized as Bristol Stool Chart data in ePRO was not collected in Study M14-347.

The following efficacy variables are not mentioned in the protocol but are added to the SAP:

Proportion of subjects with CD related hospitalization: CD related hospitalization is a component of major CD related event.

Proportion of subjects with CD related surgery: CD related surgery is a component of major CD related event.

The following efficacy endpoints are added because they are used in new CD studies.

Proportion of subjects who achieve symptomatic remission, defined as average daily stool frequency ≤ 2.8 (and not worse than Study M14-115 Baseline) and average daily abdominal pain ≤ 1.0 (and not worse than Study M14-115 Baseline) over time among subjects with Study M14-115 Baseline average daily stool frequency ≥ 4.0 or average daily abdominal pain ≥ 2.0 : This endpoint is used for new CD studies as a primary efficacy endpoint.

Proportion of subjects with a decrease in SES-CD $> 50\%$ from Study M14-115 Baseline (or for subjects with an SES-CD of 4 at Study M14-115 Baseline, at least a 2-point reduction from Study M14-115 Baseline) at Week 40.

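### Against the supplied protocol (Amendment 2), the SAP's primary responder definition is narrower, and SAP 12.1 neither logs the difference nor names the protocol version it compares with

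*SAP*

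**What the plan says.** **Protocol.** Section 5.3.3.1 defines the primary variable as an SES-CD of at most 4 "with an Ulcerated Surface subscore no greater than 1 in any segment, at Week 40 among subjects with endoscopic improvement at Week 0". The definitions table in 5.3.3 and the statistical section 8.1.4.1 use the same rule. It needs no change from an earlier score and limits only the Ulcerated Surface variable.

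**SAP.** Section 6.0 defines endoscopic improvement as SES-CD of at most 4 plus "at least two point reduction from Study M14-115 Baseline and no subscore > 1 in any individual variable". Section 10.3 repeats this for the endpoint without the Week 0 restriction: "defined as an SES-CD ≤ 4 and at least 2 point reduction versus Study M14-115 Baseline and no subscore greater than 1", again applied to each variable separately. Section 10.2 states the primary variable as the "proportion of subjects with endoscopic improvement at Week 40 among subjects with endoscopic improvement at Week 0 of Study M14-347", so the SAP rule sets both ends of the proportion. The SES-CD scoring text in 6.0 confirms that the M14-115 Baseline score enters the determination.

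**Change log.** SAP 12.1 compares the SAP with the latest protocol version but gives no amendment number or date. It lists dropped and added variables. The definition of endoscopic improvement is not among them.

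**Corticosteroid endpoints.** Protocol 5.3.3.2 bases both on subjects taking corticosteroids at Week 0 of M14-115. SAP 6.0 and 10.3 base both on users at Week 0 of M14-347.

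**The concern.** The trial has no control arm, and SAP 10.1 plans no tests. One proportion with its 95% confidence interval is therefore the whole primary result, and a reader must be able to tell which responder it describes. If the governing protocol keeps the Amendment 2 rule, the SAP proportion describes a different set of subjects at Week 0 and at Week 40, and the protocol's own primary endpoint is reported nowhere. SAP 12.1 is where this should be explained, and it is silent. No error rate or power is at stake.

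The corticosteroid endpoints raise a similar question. Protocol 5.1 says the taper began during M14-115. A subject who finished it before Week 0 of M14-347 is in the protocol denominator and outside the SAP denominator.

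**Working it through.** **1. Nesting.** Ulcerated Surface is one of the SES-CD variables, so a limit of 1 on every variable implies a limit of 1 on Ulcerated Surface. The cut-off of 4 is common to both rules. Every SAP responder is thus a protocol responder. The reverse fails, for example, for a subject whose only non-zero score is a 2 on another variable.

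**2. Effect of the 2-point fall.** With M14-115 Baseline B, the SAP needs a visit total of at most min(4, B − 2).

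| Baseline B | SAP cut-off | Protocol responders who always fail the SAP rule | Protocol responders who fail only if a variable other than Ulcerated Surface is 2 or more |
|---|---|---|---|
| 4 | 2 | totals 3 and 4 | total 2 |
| 5 | 3 | total 4 | totals 2 and 3 |
| 6 or more | 4 | none | totals 2, 3 and 4 |

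At totals 0 and 1 the rules agree for these Baselines. Where Ulcerated Surface is 2 or more, both rules fail, so they also agree there.

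The SAP itself foresees a Baseline of 4 (10.3: "or for subjects with an SES-CD of 4 at Study M14-115 Baseline, at least a 2-point reduction from Study M14-115 Baseline"), so the fall condition can bind. The documents do not give the M14-115 entry criteria, and SAP 6.0 sets missing M14-115 Baseline variables to 0, so lower Baselines cannot be excluded. There the cut-off falls further: 1 at Baseline 3 and 0 at Baseline 2.

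**3. Check by enumeration.** Assumption, since the scoring appendices are not legible: 20 items (4 variables in 5 segments), each scored 0 to 3. Of 10,606 score profiles with a total of at most 4, 9,466 meet the protocol rule and 6,196 meet the SAP limit on individual variables before the fall condition. All 6,196 lie inside the 9,466. Profiles that fail both rules through Ulcerated Surface number 100 of 1,540 at total 3 and 1,035 of 8,835 at total 4. These are counts of profiles, not of patients.

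**4. Direction.** Let the protocol rate be S/D. Let R subjects leave the Week 0 denominator under the SAP rule, K of them being protocol successes at Week 40. Let L be the remaining protocol successes who fail the SAP rule at Week 40. Then

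SAP rate = (S − K − L)/(D − R),

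which is above S/D if (K + L)/R < S/D and below it if (K + L)/R > S/D. If R, K and L are all 0, nothing changes.

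Illustration with every input assumed: D = 80, S = 48 (60.0%), R = 8, L = 0. The break-even is K = 8 × 0.60 = 4.8.

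| K | SAP rate |
|---|---|
| 0 | 48/72 = 66.7% |
| 4 | 44/72 = 61.1% |
| 5 | 43/72 = 59.7% |
| 8 | 40/72 = 55.6% |

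**5. Which protocol version did the SAP use?**

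Signs of a later version than Amendment 2:
- The supplied synopsis is dated 04 December 2014 and the SAP 13 Nov 2017.
- SAP Table 2 has a chest X-ray row and note for Ukraine that Amendment 2 lacks. The note cites a Section 5.4.1, which exists in the protocol but not in the SAP.
- Note c of Table 2 places the ileocolonoscopy at Week 24 in Amendment 2 and at Week 40 or premature discontinuation in the SAP. This sign is weak, because Amendment 2's own Section 5.1 already agrees with the SAP.
- SAP 12.1 says "change in Bristol Stool Scale score from Baseline over time will not be summarized", yet Amendment 2 lists no such endpoint.
- SAP 12.1 logs as new the "symptomatic remission, defined as average daily stool frequency ≤ 2.8 (and not worse than Study M14-115 Baseline") version. It does not log the version with a limit of 1.5, symptomatic response, SES-CD of at most 2 or SES-CD of at most 3. None of these is in Amendment 2.

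Sign that the comparator still carries Amendment 2 text: SAP 12.1 treats the predicted-improvement endpoints as present in the protocol and says they "will not be summarized as they were removed from Study M14-115 protocol".

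**The case against.** The strongest reply is that the SAP was compared with a later amendment that is not among the supplied documents. SAP 12.1 logs items as small as CD-related hospitalization and surgery. Several larger departures from Amendment 2 go unlogged, and the simplest explanation is that they were already in the protocol by then. The new definition may be one of them. The predicted-improvement endpoints do not refute this, since a version could keep them and still change the primary definition. In addition, the copy of the SAP available for review lacks pages before its table of contents and at its end, so a version reference there cannot be excluded. All of this stands, and it is why most of the fix is conditional. It does not remove the gap in 12.1, which as written does not let a reader trace the primary definition to any protocol version.

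It can also be said that the SAP definition is explicit and the analysis descriptive. Both are true, but neither tells the reader how the reported rate relates to the protocol's.

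Two stronger readings are tempting. One is that the primary endpoint was changed without documentation, or after data had been seen. The documents do not support that: a later amendment may hold the change, and nothing supplied dates it. Central reading of endoscopies, the requirement in Protocol 8.1 to finalize the SAP before database lock, and the interim analysis in Protocol 8.1.7 do not settle the matter in either direction. The other is that a narrower definition must give a lower, more cautious rate. It need not, because the denominator shrinks too.

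**Conclusion.** The point holds as a difference from the supplied protocol that cannot be traced. Against Amendment 2, the SAP's responder set is strictly narrower at Week 0 and at Week 40, and SAP 12.1 neither records this nor identifies its comparator. That much rests on the text alone.

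The size is unknown. For Baselines of 4 or more, only protocol responders with totals of 2 to 4 can be reclassified. The fall condition binds only at Baselines below 6, while the limit on all variables can bind at any Baseline. The 55.6% to 66.7% range shows only that either direction is possible.

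Whether the protocol's own primary endpoint goes unreported depends on which protocol version governs. The corticosteroid denominators carry the same condition, and their effect cannot be sized either. The move from at least 50% to more than 50% in the endoscopic-response and fistula cut-offs, and the dropped time-in-remission, time-to-remission and de-escalation endpoints, are matters for the log only.

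**What to change.** In every case, state in SAP 12.1 the number and date of the protocol version compared.

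If that version is a later amendment that already holds the SAP definition, cite it; no second primary rate is needed. Otherwise:

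- Log the change of definition with its date and reason.
- Report the primary proportion with its 95% confidence interval under the Amendment 2 definition, at Week 0 and Week 40, as a sensitivity analysis beside the SAP result. Use the same non-responder imputation and the same analysis handling of dose escalation.

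On the same test for their own definitions, report the two corticosteroid endpoints with the M14-115 Week 0 denominator beside the SAP one, and log the changed cut-offs and dropped endpoints.

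The cost is one line in all cases. If the condition applies, add some log entries and a few tables from data already collected. The real burden is having two primary-type rates to explain, so the report should say in advance which one is primary.
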